## 8.4 Subgroup analysis

Subgroup summaries will be performed for the efficacy variables of ACR and PASI response at PA0009 Week 48 for the FAS. Subgroups are defined in Section 4.8.

Subgroup summaries will be based on data following NRI only.

## 8.5 Impact of COVID-19

Additional sensitivity analyses as a result of the global COVID-19 pandemic are not anticipated as the onset of the pandemic was subsequent to all subjects completing Week 48; therefore, there is no impact on the analysis of the secondary efficacy endpoint.

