### 4.2 Handling of missing data

#### 4.2.1 Handling of missing data for efficacy analysis

Calculation of derived efficacy variables in the presence of missing data is described in individual subsections of [Section 8.1](#). All derived efficacy variables will be calculated using observed data, and any resulting missing data will be handled as described in this section. All nonresponder imputation (NRI) and MI imputation as described below will be performed only for subjects in the FAS for PA0009.

Additional methods for deriving the PASI response in the presence of missing data are described in [Section 4.2.2](#).

For assessments missing during PA0008, which were to be used in PA0009 for reporting maintenance of response, the following approach will be used:

- For summaries of binary data following NRI, the imputed value from the PA0008 database will be used.
- For summaries of non-imputed (OC) data, the assessment will be left as missing.

For all visits in PA0009 (including PA0009 EV), missing values for binary secondary/other efficacy variables (ACR20, ACR50, ACR70, PASI75, PASI90, PASI100, MDA) or values, which cannot be constructed (eg, for ACR either tender joint count [TJC]/swollen joint count [SJC] are missing or >2 out of the 5 remaining core set measures are missing) will be imputed using NRI. For each visit, subjects with missing data or who have dropped out of the study will be counted as nonresponders. This includes any subjects with missing Baseline values. For PASI response, NRI will be implemented only for subjects with BSA  $\geq 3\%$  at PA0008 Baseline.

For missing continuous secondary/other efficacy variables an MI approach will be used. This will be performed for the following endpoints:

- TJC and SJC

- Psoriasis Area and Severity Index (PASI)
  - For PASI the MI model will be restricted to subjects with a BSA affected by psoriasis of  $\geq 3\%$  at PA0008 Baseline. Subjects with a BSA affected by psoriasis of  $< 3\%$  at PA0008 Baseline will be excluded prior to performing the procedure outlined below.
- Patient's Global Assessment of Disease Activity (PGADA)
- Physician's Global Assessment of Disease Activity (PhGADA)
- Patient's Assessments of Arthritis Pain (PtAAP)
- Health Assessment Questionnaire – Disability Index (HAQ-DI)
- CRP

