### 5.1.1 Impact of COVID-19

A listing of all visits affected by COVID-19 will be presented based on the Enrolled Set including the visit, date of visit, relationship to COVID-19, impact category and a narrative (short description) of the event. This data will be summarized by treatment group at completion of PA0008, and overall for the ES for the following:

- Impact of COVID-19 for any reason
- Impact of COVID-19 for any reason by country

In addition, in order to assess the potential impact of COVID-19 on the collection and reporting of efficacy data a separate listing and summary will be presented to display missing data and data collected via an alternative modality (eg, phone, video call). For the purpose of these displays, missing data will be presented only for visits affected by COVID-19 (as reported on the dedicated eCRF page) ie, missing data at other visits and for other reasons will not be included.

The following efficacy assessments may be collected remotely:

- HADS
- HAQ-DI
- SF-36
- PGADA
- PtAAP
- PsAID-9

For visits conducted remotely (as reported on the dedicated eCRF page), it is not possible to assess MASES, PhGADA, BSA, PASI, LDI, TJC or SJC, and therefore these assessments will be missing at the specified visit. In addition, for any missed visit or a visit conducted remotely, the CRP assessment will also be missing. Such assessments will be considered to be missing as a result of COVID-19. For these visits, it will therefore not be possible to assess DAS28(CRP) and may not be possible to classify the subject as an ACR responder or nonresponder.

A listing will be presented showing each impacted visit based on the FAS. This will include the planned visit, the visit date, and details of the assessments conducted remotely and/or those missing as a result of COVID-19.

These data will be presented in a summary table by treatment group at completion of PA0008 and overall for the FAS.

For both the listing and the summary table, only visits at which efficacy assessments are scheduled will be included.

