### 8.3.1 Maintenance of response

ACR20, ACR50, ACR70, PASI75, PASI90 and PASI100 response relative to PA0008 Baseline will, in addition, be summarized at each post-Baseline visit in PA0008 through to PA0009 Week 104, by treatment sequence, as defined in Section 3.7. These summaries will be restricted to subjects in the FAS and who were responders for the relevant endpoint at PA0008 Week 12, and data will be reported following NRI.

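### SAP 8.5 waives COVID-19 efficacy sensitivity analyses on grounds that hold only for Week 48, while the maintenance tables and the ACR50-by-ADAb figures use later visits under NRI alone

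*SAP*

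**What the plan says.** SAP 8.5 states "Additional sensitivity analyses as a result of the global COVID-19 pandemic are not anticipated as the onset of the pandemic was subsequent" to Week 48 for all subjects, and its conclusion goes no further than the secondary endpoint: "subsequent to all subjects completing Week 48; therefore, there is no impact on the analysis of the secondary efficacy endpoint".

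SAP 8.3.1 has ACR20/50/70 and PASI75/90/100 "summarized at each post-Baseline visit in PA0008 through to PA0009 Week 104, by treatment sequence", restricted to FAS subjects "who were responders for the relevant endpoint at PA0008 Week 12, and data will be reported following NRI". No other missing-data method is named there. SAP 9.2 likewise bases its two figures of ACR50 over time by ADAb status on NRI.

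For remote visits SAP 5.1.1 says "it is not possible to assess MASES, PhGADA, BSA, PASI, LDI, TJC or SJC, and therefore these assessments will be missing at the specified visit". It adds that CRP is missing at remote and missed visits alike, and accepts that ACR response may then be unclassifiable. It plans a listing and a summary table, on the FAS, of efficacy data missing or collected remotely because of COVID-19.

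The NRI rule in SAP 4.2.1 is "For each visit, subjects with missing data or who have dropped out of the study will be counted as nonresponders".

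The observed-case (OC) and multiple-imputation (MI) versions in SAP 8 and 8.3 belong to the by-visit ACR and PASI tables, presented by treatment group at completion of PA0008.

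**The concern.** SAP 10.2.4 dates the pandemic from 11 March 2020 and expects it to be ongoing at the last subject's last visit. Visits after Week 48 are therefore exposed, and the reason given in 8.5 does not cover them. Where an output has only an NRI version, a subject who is still dosed and well but was seen by telephone appears at that visit as someone who has lost response. SAP 5.1.1 treats the same data as missing because of COVID-19.

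What is at stake is how the late part of the maintenance tables is read. The SAP added these tables itself (3.10) to inform the long-term efficacy objective. They are the only outputs restricted to PA0008 Week 12 responders and split by treatment sequence, so the by-visit OC and MI tables do not stand in for them.

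**Working it through.** **1. What a remote visit does to ACR.** Under SAP 5.1.1, TJC, SJC, PhGADA and CRP are missing; PGADA, PtAAP and HAQ-DI may be collected remotely. Applying SAP Table 12-1 with both joint counts missing and those three components present:

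| Patient-reported components improved | ACR result | Worst-case flag |
|---|---|---|
| 3 | N | yes |
| 2 | N | yes |
| 1 | N | yes |
| 0 | N | no |

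Every row gives N, so a true responder cannot be counted as one. A fully missed visit (no components) is also N, with the flag.

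**2. PASI.** The score is missing at a remote or missed visit, so PASI75/90/100 are nonresponse under NRI. The supplementary PASI rules in SAP 4.2.2 rely on BSA, which is also missing at a remote visit, and SAP 8.3 does not apply them to the maintenance tables.

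**3. Which visits can fall in the pandemic.** These are nominal dates, ignoring visit windows.
- Week 104 falls on or after 11 March 2020 for a first PA0009 dose on or after 11 March 2020 − 728 days = 14 March 2018.
- Week 60 does so for a first dose on or after 11 March 2020 − 420 days = 16 January 2019.
- If all subjects had passed Week 48 by 10 March 2020, the latest possible first dose is 10 March 2020 − 336 days = 9 April 2019. That puts Week 104 no later than 9 April 2019 + 728 days = 6 April 2021.

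Visits from Week 60 to Week 104 can therefore be affected. The entry dates themselves are not in the documents, so the April dates are upper bounds.

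**4. Size.** The plan states no figure to reproduce. Let *p* be the true maintenance rate at a visit and *c* the share of Week 12 responders whose assessment is missing because of COVID-19, with missingness unrelated to response. Then the NRI rate = *p* × (1 − *c*). Both *p* and *c* are assumed:

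| *p* | *c* = 5% | 10% | 20% | 30% |
|---|---|---|---|---|
| 70% | 66.5% | 63.0% | 56.0% | 49.0% |
| 80% | 76.0% | 72.0% | 64.0% | 56.0% |
| 90% | 85.5% | 81.0% | 72.0% | 63.0% |

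The understatement is *p* × *c*, from 0.70 × 0.05 = 3.5 points to 0.90 × 0.30 = 27 points.

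**5. Is NRI really the only method?** SAP 8.3.1 names only NRI, and no OC or MI maintenance output is listed in Sections 8 to 8.3.1. SAP 4.2.1 is less consistent. It gives an OC rule for PA0008 assessments used for maintenance. Its MI text describes maintenance summaries showing PA0008 as well as PA0009 visits, and later it confines all MI summaries to the PA0009 entry visit onwards. These statements cannot all describe the same set of tables.

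**The case against.** The strongest reply is that the gap is narrow, and that stands. Maintenance is an 'other' efficacy variable added to the protocol's list, in a descriptive single-arm safety study. The by-visit ACR and PASI tables to Week 104 already have OC and MI versions, and SAP 5.1.1 will show which efficacy assessments COVID-19 removed. Section 8.5 is right for the Week 48 variables and claims no more than that.

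The effect is also confined to the affected visit. NRI is applied visit by visit, so a subject can be a responder again at the next on-site visit, and SAP 3.5 lets an unscheduled on-site assessment within the window be mapped in.

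Two stronger readings are tempting and should not be drawn:
- A reader might infer that the loss falls systematically more on some treatment sequences, through entry date or country. PA0008 was randomized and the sequences follow from its treatments, so these factors are balanced in expectation. Chance imbalance in small groups is possible, but the documents show none.
- A reader might divide 200 subjects by seven sequences to get a loss in points per sequence. But 200 is a ceiling, and SAP 3.7 shows five starting regimens of which only placebo and 16mg split in two, so equal sequence sizes do not follow. No Week 12 responder rate is given, and one rate would not suit both the placebo and the active sequences.

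The uneven wording in 4.2.1 might suggest that OC or MI maintenance tables were intended. None is specified, so this is a reason to clarify and does not answer the point.

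**Conclusion.** The concern holds in a limited form. The Week 48 rationale is the only reason given for having no COVID-19 efficacy sensitivity analysis, while the maintenance tables and the two ACR50-by-ADAb-over-time figures use later visits under NRI alone. A responder whose late visit was remote or missed because of COVID-19 is counted as a nonresponder at that visit, so late maintenance can be understated.

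The amount is unknown. A fall from 80% to between 76% and 56% rests on an assumed true rate, an assumed 5% to 30% of assessments affected, and missingness unrelated to response. No primary or secondary conclusion depends on it. The documents do not support extending the point to the Week 48 endpoints, to permanent loss of response, or to COVID-19 handling in general.

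**What to change.** - **SAP 8.3.1:** keep NRI. Add a supplementary maintenance table for PA0009 visits in which assessments that are actually missing at visits flagged on the COVID-19 eCRF page are not scored as nonresponse. The flag alone is not enough, because the page in SAP 12.6 also records home visits, out-of-window visits and dosing-only events.
- **Method:** either remove the affected subject-visits from the denominator, or use the MI-derived ACR and PASI responses already planned in 4.2.1. If MI is used, note that its model is fitted by treatment group at completion of PA0008 and not by sequence, so imputed values borrow across the sequences the table separates. Plain OC is not sufficient. Under Table 12-1 it keeps remote visits with no improved patient-reported component as nonresponders and drops the rest, which still pulls the rate down. The exclusion should cover all affected visits.
- **SAP 9.2:** repeat the ACR50-by-ADAb-over-time figures the same way. This does not repair the ADAb grouping: a subject with no positive sample and two or more missing samples goes to the missing group, so add a footnote saying so.
- **SAP 8.5:** limit the sentence to the Week 48 secondary endpoints.
- **SAP 4.2.1:** reconcile the OC and MI wording on maintenance with 8.3.1.

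The cost is a few extra tables and figures and some text edits, using flags already collected. The MI option also needs a combined NRI/MI dataset that is not yet planned. The downside is two versions to explain.

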## 9 PHARMACOKINETICS AND PHARMACODYNAMICS

### 9.1 Pharmacokinetics

Bimekizumab plasma concentrations will be summarized at each scheduled visit in PA0009 by treatment at completion of PA0008 and overall, using the SS.

If bimekizumab plasma concentration measurements are deemed to be below the level of quantification (BLQ), then for calculation of the derived statistics this sample result will be set to half the LLOQ. Descriptive statistics will be calculated only if at least 2/3 of the values are above the LLOQ at a given visit. If this is not the case, only median, minimum, and maximum will be presented.

In addition, geometric mean bimekizumab plasma concentration (with 95% CI) time curves will be plotted versus time on linear and semi-logarithmic scales by treatment group at completion of PA0008.

The summary tables for bimekizumab plasma concentrations will display n, geometric mean (and 95% CI), geometric CV%, arithmetic mean, SD, median, minimum, and maximum, where the geometric CV% is calculated using the following formula:

$$CV\% = \sqrt{e^{SD_n^2} - 1} \times 100 \quad (17)$$

where  $SD_n$  represents the standard deviation of the ln-transformed plasma concentration values.

Geometric mean plots will be repeated by cumulative ADAb positivity and treatment:

- The ADAb positive status will be considered in a cumulative manner at each time point (ie, if a subject has had at least 1 positive sample at any time point up to and including the given time point, that subject would be counted as positive at that time point, regardless of any subsequent negative measurements). Thus, the number of subjects included in the geometric mean for positive and negative categories will vary by time point for each treatment.
- Two plots will be presented each displaying bimekizumab plasma concentration data in PA0009 only:
  - Considering cumulative ADAb status in PA0009 only at each time point in PA0009
  - Considering cumulative ADAb status in PA0008 and PA0009 at each time point in PA0009
- Each plot (linear and semi-logarithmic) will be presented by treatment group at completion of PA0008 and ADAb positive status (4 lines per plot)

The following rules will be implemented for PK concentration summaries and corresponding figures:

- If the dosing for a visit is performed more than 14 days prior to, or more than 14 days after the scheduled dosing interval (28 days), then the plasma concentration obtained at that dosing visit will be excluded from the PK summaries and figures. Thus, if the dosing interval is less than 14 days or greater than 42 days, this rule will apply. This will also apply to doses administered at an unscheduled visit.
- If a PK sample is collected >14 days after the preceding dose and up to 1 hour after the dose at the current visit, the PK concentration for that sample will be associated with the current visit and summarized accordingly. This will include unscheduled assessments as described in [Section 3.5](#) (if a dose was administered at an unscheduled visit). Samples collected outside this window will be excluded from the PK summaries and figures and will be listed only.
- Individual samples collected at a scheduled visit at which dosing was not performed (eg, due to AE) will be retained in the PK summaries and figures for the specific visit if these are collected >14 days and <42 days after the preceding dose, as these reflect the trough concentration from the preceding dose. The sample obtained at the subsequent scheduled visit will be excluded from the summaries (regardless of dosing) as this will not reflect a steady-state trough concentration (as the previous dose was not administered). Thereafter PK samples will be included in the summaries assuming dosing has resumed and the sample was obtained within the required window of >14 days after the preceding dose and up to 1 hour after the dose at the current visit.
  - Note samples collected at Week 104 will be retained in the PK summaries and figures if they are collected >14 days and <42 days after the last dose received
  - Note samples collected at the ET visit will be retained in the PK summaries and figures if they are collected >14 days and <42 days after the last dose received

These rules will not apply for the SFU visit as no dosing is planned at this visit. All concentrations obtained at the SFU visit will be included in the summary tables (but will not be included in the figures).

Bimekizumab plasma concentrations will be listed for the SS, separately for PA0009 and for data from PA0008 and PA0009 combined. All concentrations will be listed as received, prior to substitution of any BLQ values. The listing of the PA0009 data will include flags for concentrations that were excluded from the summary statistics where the reason for exclusion will be one of the following:

- Dosing performed out of window
- Sample collected out of window relative to current dose
- Sample collected out of window relative to previous dose
- Missed dose at preceding visit (in conjunction with one of the above reasons)
- More than one sample obtained at the same visit

All plasma concentration data will be reported in ug/mL in the tables, figures, and listings.

## 9.2 Pharmacodynamics and Immunogenicity

The immunological variable is ADAb evaluated at scheduled visits up to 104 weeks in accordance with the schedule of study assessments (Table 2-1).

ADAb will be assessed using a tiered approach: screening, confirmatory, and titer assays will be used.

Samples will first be evaluated in the screening assay using a false positivity rate of 5% (reported as 'above the cut-point' ACP or 'below the cut-point' [BCP]), followed by analysis of screened positive samples (reported as ACP) in the confirmatory assay (which is a drug depletion assay) to confirm the true positivity of the samples (reported as either 'confirmed positive' [CP] or 'not confirmed positive' [NCP]). Samples that are CP will be evaluated in a titration assay to quantify the ADA level and will be reported as titer (reciprocal dilution factor including minimum required dilution [MRD]). Screening, confirmatory and titer cut points of the respective assays will be determined by the bioanalytical laboratory which will report the bioanalytical result from the respective assays.

The following rule will be implemented for by-visit ADAb summaries where applicable:

- If the ADAb sample is collected within  $\pm 21$  days relative to the visit date at which the drug was administered (or  $\pm 21$  days from a scheduled visit at which dosing was not performed), the ADAb result for that sample will be associated with the scheduled visit and summarized accordingly. This will include unscheduled assessments as described in Section 3.5 (if a dose was administered at an unscheduled visit). Samples collected outside this window will be excluded from the ADAb summaries and figures and will be listed only.

The rule above will apply to by-visit summaries only; summaries of cumulative ADAb status and time to treatment-emergent positivity will use all available data. This rule will not apply for Visit 13 (Week 104), ET visit or the SFU visit as no dosing is planned at these time points. All ADAb data obtained at these visits will be included in the by-visit summaries.

ADAb status will be derived as follows:

- Samples that are either BCP or ACP and NCP will be defined as **ADAb negative**.
- Sample values that are ACP and CP will be defined as **ADAb positive** (regardless of whether or not a titer is available)

In addition, the ADAb status will be further classified on a subject level as outlined below:

- **Pre ADAb negative – treatment emergent ADAb negative (Category 1):**
  - Considering PA0009 data only (Category 1a): includes subjects who are ADAb negative at PA0008 Baseline and ADAb negative at all sampling points in PA0009 (including SFU).
  - Considering PA0008 and PA0009 data (Category 1b): includes subjects who are negative at PA0008 Baseline and ADAb negative at all sampling points in PA0008 and PA0009 (including PA0009 SFU).
- **Pre ADAb negative – treatment emergent ADAb positive (Category 2):**

- Considering PA0009 data only (Category 2a): Includes subjects who are negative at PA0008 Baseline and ADA b positive at any sampling point post treatment in PA0009 (up to and including SFU and including the PA0009 EV). This group also includes subjects who have a missing pre-treatment sample (either missing or insufficient volume) at PA0008 Baseline with one or more ADA b positive samples in PA0009.
- Considering PA0008 and PA0009 data (Category 2b): Includes subjects who are negative at PA0008 Baseline and ADA b positive at any sampling point post treatment in PA0008 (up to and including PA0009 SFU). This group also includes subjects who have a missing pre-treatment sample (either missing or insufficient volume) at PA0008 Baseline with one or more ADA b positive samples in PA0008 or PA0009.
- **Pre ADA b positive – treatment emergent reduced ADA b (Category 3):**
  - Considering PA0009 data only (Category 3a): Includes subjects who are positive at PA0008 Baseline, and ADA b negative at all sampling points in PA0009 (including SFU).
  - Considering PA0008 and PA0009 data (Category 3b): Includes subjects who are positive at PA0008 Baseline, and ADA b negative at all sampling points in PA0008 and PA0009 (including SFU).
- **Pre ADA b positive – treatment emergent unaffected ADA b positive (Category 4):**
  - Considering PA0009 data only (Category 4a): Includes subjects who are positive at PA0008 Baseline and are positive at any sampling point in PA0009 (including SFU) with titer values of the same magnitude as PA0008 Baseline (ie, less than a predefined fold increase from the PA0008 Baseline value defined within the validation of the assay).
  - Considering PA0008 and PA0009 data (Category 4b): Includes subjects who are positive at PA0008 Baseline and are positive at any sampling point in PA0008 or PA0009 (including SFU) with titer values of the same magnitude as PA0008 Baseline (ie, less than a predefined fold increase from the PA0008 Baseline value defined within the validation of the assay).

For the purposes of this study, this is set at an increase of less than or equal to a 3-fold difference from PA0008 Baseline.

- **Pre ADA b positive – treatment emergent ADA b boosted positive (Category 5):**
  - Considering PA0009 data only (Category 5a): Includes subjects who are positive at PA0008 Baseline and are positive at any sampling point post treatment in PA0009 (including PA0009 EV and SFU) with increased titer values compared to PA0008 Baseline.
  - Considering PA0008 and PA0009 data (Category 5b): Includes subjects who are positive at PA0008 Baseline and are positive at any sampling point post treatment in PA0008 or PA0009 (including SFU) with increased titer values compared to PA0008 Baseline.

The increase in titer values is defined as an increase greater than a predefined fold increase from PA0008 Baseline value which is defined within the validation of the assay. For the

purposes of this study, this is set at an increase greater than a 3-fold difference (ie, a minimum of a 4-fold increase).

Note: For any subject who is positive at PA0008 Baseline and positive at a post-Baseline time point, but for whom titers are not available to determine treatment unaffected or treatment boosted status, the subject will be considered as treatment boosted (ie, Category 5), assuming no other samples are available.

- **Inconclusive (Category 6):**
  - Considering PA0009 data only (Category 6a): Includes subjects who have a positive pre-treatment sample at PA0008 Baseline and some PA0009 samples are missing, while other PA0009 samples are ADA b negative.
  - Considering PA0008 and PA0009 data (Category 6b): Includes subjects who have a positive pre-treatment sample at PA0008 Baseline and some PA0008 or PA0009 samples are missing, while other PA0008 and PA0009 samples are all ADA b negative.
- **Total treatment-emergent (Category 7 [Categories 2 and 5 combined]):**
  - Considering PA0009 data only (Category 8a): Includes subjects who are pre ADA b negative – treatment emergent ADA b positive (Category 2a) and pre ADA b positive – treatment boosted ADA b positive (Category 5a).
  - Considering PA0008 and PA0009 data (Category 8b): Includes subjects who are pre ADA b negative – treatment emergent ADA b positive (Category 2b) and pre ADA b positive – treatment boosted ADA b positive (Category 5b).
- **Total pre ADA b positive (Category 8 [Categories 3, 4, 5 and 6 combined]):** Subjects that are tested ADA b positive at PA0008 Baseline.
- **Missing (Category 9):**
  - Considering PA0009 data only (Category 9a): Includes subjects who have a missing or negative pre-treatment sample at PA0008 Baseline and some PA0009 samples are missing, while other PA0009 samples are ADA b negative.
  - Considering PA0008 and PA0009 data (Category 9b): Includes subjects who have a missing or negative pre-treatment sample at PA0008 Baseline and some PA0008 or PA0009 samples are missing, while other PA0008 and PA0009 samples are all ADA b negative.

The following summaries, figures and listings will be produced:

- Summary tables displaying the number and percentage of subjects with a positive ADA b status at each PA0009 visit and at any visit by treatment group at completion of PA0008. Two tables will be presented:
  - Considering ADA b status in PA0009 only
  - Considering ADA b status in PA0008 and PA0009 (this table will include only the overall summary visits as detailed below).

For the overall summary at any visit 2 summaries will be presented as follows (all summaries exclude data obtained at PA0008 Baseline):

- PA0009 data only: Including any visit during the PA0009 treatment period (as defined in [Section 3.2.2](#)). Thus, this summary will exclude data obtained at the SFU visit and will include data obtained at the PA0009 EV.
- PA0009 data only: Including any visit during PA0009. Thus, this summary will include both data obtained at the SFU visit and at the PA0009 EV.
- PA0008 and PA0009 data: Including any visit during the PA0008 and PA0009 treatment period. Thus, this summary will exclude data obtained at the PA0009 SFU visit.
- PA0008 and PA0009 data: Including any visit during PA0008 and PA0009. Thus, this summary will include data obtained at the PA0009 SFU visit.
- Summary tables (by treatment at completion of PA0008) of the time point of the first occurrence of ADA b treatment-emergent positivity during PA0009, including the PA0009 EV and the SFU visit. This summary will include the following categories:
  - Category 2: Pre ADA b negative – treatment-emergent ADA b positive
  - Category 5: Pre ADA b positive – treatment-boosted ADA b positive

The table will summarize the number and percentage of subjects who are either treatment-emergent ADA b positive or treatment-boosted ADA b positive for the first time at the specified time point in PA0009 and will include the cumulative number and percentage of subjects with treatment-emergent ADA b positive results at each time point.

The table will be repeated considering ADA b status at each visit in both PA0008 and PA0009 and will therefore display all visits in both PA0008 and PA0009.

An additional table will be presented considering ADA b status at each visit in both PA0008 and PA0009, and will be presented by treatment at randomization in PA0008.

- Summary tables displaying the number and percentage of subjects in each of the ADA b categories as defined above by treatment at completion of PA0008. Two tables will be presented:
  - Considering data from PA0009 only
  - Considering data from PA0008 and PA0009
- The time to achieving treatment-emergent ADA b positivity in PA0009, separated by treatment group at completion of PA0008, will be graphically presented. Subjects will be considered to have an event at the time point at which treatment-emergent ADA b positivity is first achieved. The plot will display the cumulative percentage of subjects with treatment-emergent positivity and will include the following categories (4 lines per plot):
  - Category 2: Pre ADA b negative – treatment-emergent ADA b positive
  - Category 5: Pre ADA b positive – treatment-boosted ADA b positive
    - Category 2 and Category 5 subjects will be combined in 1 group (2 lines per plot) if the percentage of subjects in each treatment group in Category 5 is <10%.

The figure will be repeated considering data from both PA0008 and PA0009 and will therefore display all visits in both PA0008 and PA0009.

In the event that  $\geq 10\%$  of subjects in either treatment group are classified as Category 5 the figure will be presented by treatment and ADA b status (4 lines per plot). This will be implemented for both plots (considering only PA0009 and considering data from both PA0008 and PA0009).

An additional figure will be presented considering data from both PA0008 and PA0009, and will be presented by treatment at randomization in PA0008 (for this figure the 160mgLD and 160mg treatments will be pooled). This figure will be presented as follows:

- If  $< 10\%$  of subjects in each treatment group (based on treatment at randomization) are classified as Category 5, the figure will be presented with 5 lines on 1 plot (1 for each treatment) and both categories combined
- If  $\geq 10\%$  of subjects in any treatment group (based on treatment at randomization) are classified as Category 5, the figure will be presented by category and treatment at randomization with separate plots (each with 5 lines) for each category
- A summary of efficacy response (ACR50 responders [based on NRI]) as a function of ADA b titer will be presented graphically. The x-axis will display the ADA b titer at the Week 48 time point (categorized as negative, Q1, Q2, Q3 and Q4 where the latter represents the quartiles for the ADA b titers at Week 48) and the y-axis will display percentage of ACR50 responders at the Week 48 time point within each titer category.

Subjects with negative ADA b results at the Week 48 time point will be included in the 'negative' category on the x-axis; subjects with missing ADA b data at the Week 48 time point will be excluded from the plot. The figure will be based on the FAS.

- A summary of efficacy response (ACR50 responders) versus time will be presented graphically including the following ADA b groups (3 lines per plot):
  - ADA b positive
    - Defined as subjects having at least 2 ADA b positive samples during PA0009 (including PA0009 EV and SFU) regardless of other ADA b negative samples and/or missing or inconclusive samples
  - ADA b negative
    - Defined as subjects for whom either (1) all samples in PA0009 (including PA0009 EV and SFU) are ADA b negative and there are no missing or inconclusive samples or (2) only 1 sample in PA0009 is ADA b positive and all other samples in PA0009 (including PA0009 EV and SFU) are ADA b negative or missing/inconclusive or (3) only 1 sample is missing/inconclusive and the remaining samples are ADA b negative.
  - Missing
    - Defined as subjects who do not fulfil the criteria for one of the 2 groups listed above.

The figure will be repeated considering ADA b status based PA0008 and PA0009 combined, with the following definitions:

- ADAb positive
  - Defined as subjects having at least 2 ADAb positive samples during PA0008 and PA0009 (excluding PA0008 Baseline and including PA0009 EV and SFU) regardless of other ADAb negative samples and/or missing or inconclusive samples
- ADAb negative
  - Defined as subjects for whom either (1) all samples in PA0008 and PA0009 (excluding PA0008 Baseline and including PA0009 EV and SFU) are ADAb negative and there are no missing or inconclusive samples or (2) only 1 sample in PA0008 or PA0009 is ADAb positive and all other samples in PA0008 and PA0009 (including PA0009 EV and SFU) are ADAb negative or missing/inconclusive or (3) only 1 sample is missing/inconclusive and the remaining samples in PA0008 and PA0009 are ADAb negative.
- Missing
  - Defined as subjects who do not fulfil the criteria for one of the 2 groups listed above.

Both figures described above will be based on the FAS and the data for ACR responders will be based on NRI. If the percentage of subjects in the missing category is  $\leq 5\%$ , this category will be omitted from the plot.

- Spaghetti plots of ADAb titer (y-axis) versus time (x-axis), separated by treatment group at completion of PA0008 for all ADAb positive subjects. This plot will include the following ADAb categories, based on data collected in PA0009:
  - Category 2: Pre ADAb negative – treatment-emergent ADAb positive
  - Category 5: Pre ADAb positive – treatment-boosted ADAb positive

Separate plots will be presented for each treatment group with both categories on the same plot. Plots will be presented using a semi-logarithmic scale for the ADAb titers (ADAb negative samples will therefore be excluded from the plot). The x-axis will reflect time from the PA0009 EV.

- Listings of individual subject-level ADAb results will be presented for the following:
  - Including only data from PA0009.
  - Including data from both PA0008 and PA0009.

The listing of PA0009 data will also include flags for ADAb measurements that were excluded from the by-visit summaries. The reason for exclusion will be one of the following:

- Sample collected out of window relative to current dose or visit
- More than one sample obtained at the same visit

Any ADAb measurements that were outside the tolerance limit of the assay will also be flagged in the listing.

All outputs described in this section will be presented using the SS, unless otherwise stated.

